2. A history of psychotic symptoms (hallucinations or delusions) in the absence of prominent mood symptoms attributable to Major Depressive or Manic Episodes, delirium, or substance use/withdrawal (see rationale above)
3. Cognitive impairment defined as a Brief Orientation Memory and Concentration Test (Katzman et al., 1983) score > 10
4. Lack of decision-making capacity to evaluate the risks versus the benefits of participation as determined by a score of <14 out of a possible 20 on up to 2 assessments using the Jeste Decision-Making Capacity Assessment – University of California, San Diego Brief

Assessment of Capacity to Consent (UBACC) (Jeste et al., 2007), or adjudication of incompetence and the appointment of a guardian or conservator

5. Six or more previous lifetime suicide attempts as ascertained through SPAN, reports from family, or patient self-report
6. Current or recent (within six months) use of lithium
7. History of significant adverse effects of lithium as ascertained through the medical record or self-report
8. Unstable medical conditions or specific medical comorbidity:
 - a. Congestive heart failure by Framingham criteria (McKee et al., 1971)
 - b. QTc greater than or equal to 450 ms for men or
QTc greater than or equal to 460 ms for women (Measurement of the QT interval and the risk associated with QTc interval prolongation: A review. Moss et al., 1993).
 - c. Chronic renal disease as defined by national Kidney Foundation Disease Outcome Quality Initiative (KDOQI) criteria (2000) with a estimated GFR less than 60 mL/min/1.73m².
9. Any possibility of being pregnant or not on appropriate birth control
10. Women who are lactating and breast feeding
11. Concurrent medications:
 - a. All diuretics except amiloride
 - b. Haloperidol
 - c. Clozapine
12. Active substance abuse:
 - a. Active alcohol or opiate dependence requiring medically supervised withdrawal and stabilization
 - b. Active cocaine, methamphetamine, other stimulant, hallucinogen, or cannabis abuse requiring stabilization
13. Enrollment and active participation in another randomized interventional clinical trial

Rationale:

Most diuretics and ACE inhibitors decrease renal excretion of lithium, potentially increasing lithium levels. The only diuretic allowed in the study is amiloride. Subjects on ACE inhibitors/AR blockers and amiloride can be admitted.

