The starting dose of lithium will be 300 mg. Subjects on antihypertensive medications will need to be on a stable dose, defined as being on the same dose of antihypertensive medication for at least one week while achieving adequate blood pressure control. Monitoring will be intensified with lithium levels obtained monthly throughout the study once they are at steady state. Patients starting diuretic (amiloride) and ACE inhibitors/AR blockers may continue study medication at a reduced dose and increased monitoring as described in “Ongoing Dose Adjustments” in Section XIII).

Patients taking haloperidol are excluded because there are concerns of specific interactions with lithium in the central nervous system. Patients taking clozapine are excluded because its indications, treatment-resistant schizophrenia and reducing recurrent suicidal behavior in schizophrenia or schizoaffective disorders, are not compatible with the inclusion criteria.

VI. STUDY MEASURES

The baseline assessment will collect basic information including race, ethnicity, educational attainment, period of military service, combat exposure, and marital status. Tables 1 and 6 summarize the other data to be collected, their source, and the estimated time required of the participant.

Primary Outcome

The primary outcome will be time to the first repeated episode of suicidal self directed violence including (non-fatal) suicide attempts and deaths from suicide over the one year follow-up period. Interrupted attempts and hospitalizations specifically for the prevention of suicide will be considered equivalent to attempts. To minimize variability and bias in identifying episodes of suicidal self-directed violence, the Outcomes Adjudication Committee will review all potential outcome events, and make final determinations about which should be considered.

The nomenclature and definitions for suicide-related behaviors will follow CDC definitions (Crosby et al., 2011). By definition, an attempt must be accompanied by a wish to die, either reported by the patient, or inferred on the basis of his or her behavior. Repeated suicide attempts are clinically significant outcomes and a proxy for death from suicide.

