Lithium will be provided as extended-release lithium carbonate (or placebo) in 300 mg tablets. Subjects will be started on 600 mg/day (300 mg bid), unless there are clinical indications for starting at a lower dose (300 mg/day). Lithium (or placebo) plasma levels will be determined (by send-out central lab testing) after each dose adjustment (see section XIV, Titration Visits, for more detail) until steady state at target plasma levels between 0.6 and 0.8 mEq/L is achieved. Steady state is defined as a serum lithium level between 0.6 and 0.8 mEq/L, over 2 consecutive visits, at the same dose, and with the second level the same or 0.1 mEq/L lower than the first level. The target range will be operationalized by providing guidance to Site Physicians that they should stop titrating the dose upwards if proportional increases in plasma levels would exceed 0.8 mEq/L, that is, if the steady state plasma level on a dose of 300 mg/day exceeds 0.40 mEq/L or the level of a dose of 600mg/day exceeds 0.53 mEq/L. After steady state levels within the target range are achieved, the frequency of plasma level determinations will be decreased to monthly until the end of six month's participation, and then quarterly unless they are on an ACE inhibitor or a diuretic, in which case monthly monitoring will continue; they will be done more frequently when medically indicated in either the lithium or the placebo group.

The target plasma levels are within the range considered effective for other lithium indications. The 2010 VA-DoD Clinical Practice Guideline for Bipolar Disorder recommends target levels of 0.6-1.0 mEq/L for maintenance treatment; the 2009 VA-DoD Clinical Practice Guideline for Major Depressive Disorder recommends 0.5-1.0 mEq/L for the augmentation of antidepressant responses; and the 2002 American Psychiatric Association Guideline on Bipolar Disorder recommends 0.5-1.2 mEq/L. A 1998 observational study by Tondo et al. found an 85-90% reduction in suicide risk for patients on lithium with average plasma levels of 0.624 ± 0.134 mEq/L. Based on these data, target plasma levels for the Lauterbach study (2008) were 0.6-0.8 mEq/L, similar to those proposed for this study.

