The process for titrating study medication at the initiation of study treatment and for maintaining them during the course of the study will be based on real or simulated plasma levels. To ensure local site blinding and standardization of measurements, some blood samples will be sent to a Central Laboratory for analysis. Lithium levels, TSH, T4, and creatinine will be analyzed by the Central Laboratory, while other samples, for complete blood count (CBC) and electrolytes will be sent to the local VA laboratories for analysis.

Lithium levels, creatinine, eGFR, and summary of side effects will be sent to the MAVERIC data coordinating center which will send real or simulated plasma levels and dosage adjustment recommendation to the Site Physician and to the Central Psychiatrist/Safety Officer. A lithium level of 1.2 or above will be considered a potentially dangerous situation and will be automatically sent to the Site Physician as well as the Coordinating Center and Central Psychiatrist/Safety Officer.

The Site Physician will use these levels and a check list review of symptoms at the time of the blood draw to make dose adjustments. During the initial dose adjustments, the Site Physician will typically decide between increasing doses by one pill per day, or maintaining the current dose.

Participants will have titration visits until they reach the target steady state: a serum lithium level between 0.6 and 0.8 mEq/L, over 2 consecutive visits, at the same dose, and with the second level the same or 0.1 mEq/L lower than the first level. It is expected that most patients will titrate within 4-6 visits, but the process may take fewer visits, or may take up to 8. If steady state is not achieved after 8 visits, the Central Psychiatrist/Safety Officer will work with the site on a case-by-case basis to determine a prescribing plan. If participants are not able to tolerate the dose needed to achieve the target level, they will be prescribed their maximum tolerated dose.

If it has been fewer than 60 days from randomization to achieving steady state, the participant's next visit will be a steady state follow-up visit 2 months after randomization (within the window allowed for steady state visits). If it takes more than 60 days, the next visit will be the 3 month steady state visit, and the month 2 visit will be omitted.

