For added safety, the site physician has the capacity to hold study medication for up to three days or decrease the dose as the clinical circumstances warrant. When determining the initial dose of study medication; if the site physician has concerns that factors such as aging, potential drug-drug interactions, or potential drug-disease interactions would decrease the tolerability of an initial dose of 600 mg of study medication, he or she could reduce the starting dose to 300 mg/day for the first interval.

During the course of the study, there may be unanticipated changes in the patient's medical condition, side effects or adverse reactions to study medication, new prescriptions of medications with potential drug-drug interactions, or other events associated with volume depletion or dehydration that could lead to adverse events through increased the serum level or increased tissue sensitivity. If any of these occur, the site physician may decrease the dose of study medication.

Whenever the site physician holds study medication or prescribes a reduced dose for reasons of safety, he or she will document the reason, and the duration of the "hold" or the actual dose prescribed. Also, at these times, the site physician will monitor the patient closely, e.g., through increased contact by telephone. Depending on the patient's clinical condition, further dose decreases may be necessary; decreases down to 300 mg/day are allowed by the protocol. If the patient is stable, the reduced dose will be maintained for approximately 5-7 days at which time another lithium level will be obtained and used to guide further dose adjustments, as appropriate.

When each patient is entered, the Research Team will forward information on physiological parameters including age, sex, height, weight, medications, medical conditions, and creatinine to the MAVERIC data coordinating center to allow estimations of the lithium clearance using empirical algorithms (e.g., Abou-Auda et al., 2008). At the time that blood levels are determined, the Research Team at the study site will provide the MAVERIC data coordinating center with updated information on laboratory parameters, information about changes in the patient's medications and medical status, and reports from the patient on adherence for study medications and side effects. To calculate the simulated lithium level, the MAVERIC data coordinating center will:

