In general, blood samples, updated medical and psychiatric history, and review of side effects will be obtained on approximately the 7th day (\pm 2 days) of the dosing interval (see section XIV, Titration Visits, for more detail). Findings will be reported to the Central Psychiatrist/Safety Officer and lithium levels (actual or simulated) under ideal circumstances will be communicated to the site within 48-72 hours.

Once the Site Physician decides on dose adjustments and orders the study medication, the blister card containing the prescribed amount of tablets will be dispensed in person or by express mail.

If, for any reason, the scheduled blood tests are missed, the process for dose adjustment will need to be modified. However, the scheduled assessments will still be completed to guide patient management as well as to ensure ongoing study assessments. The Site Physician may either hold the current dose if there are problems or continue the current dose but may not, to be cautious, increase the dose. If necessary, the subject will be mailed enough blister-packed tablets to cover the time until the next scheduled dose adjustment.

Ongoing dose adjustments

During the course of double-blind treatment a number of events may indicate the need for additional clinical assessments, blood level determinations, other laboratory tests, and, possibly, dose adjustments. These may, for example, include reports of side effects, observations of possible adverse reactions, laboratory measures, changes in medical status, or modifications in medications. When these occur, the Site Physician will conduct clinical evaluations, obtain blood for lithium level and other determinations as needed using the same procedures for planned dose adjustments. Decisions about clinical management of dosing will be the responsibility of the Site Physician. He or she may ask the patient not to take study medications for up to three days, modify the dose on a temporary basis, or modify the dose from that time onward. In general, he or she will continue to monitor the patient with repeated contacts, assessments, blood levels, and other tests as appropriate until the patient's medical status and blood levels stabilize.

Enhanced usual care for preventing suicide

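### After month 6, Protocol Section XIII leaves AR blocker users out of the monthly lithium-level rule that Section V sets for them, and Section XIV and Table 6 carry no exception for AR blocker, ACE inhibitor or amiloride users

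*Protocol*

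**What the plan says.** Four places in the protocol set the lithium-level schedule.

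- **Section V, rationale for the exclusion criteria.** On eligibility: "Subjects on ACE inhibitors/AR blockers and amiloride can be admitted". On follow-up: "Monitoring will be intensified with lithium levels obtained monthly throughout the study once they are at steady state". On participants who begin one of these drugs later: "Patients starting diuretic (amiloride) and ACE inhibitors/AR blockers may continue study medication at a reduced dose and increased monitoring", with a pointer to the part of Section XIII on ongoing dose adjustments.
- **Section XIII, Study medications.** Levels are monthly to the end of month 6 and then quarterly, "unless they are on an ACE inhibitor or a diuretic, in which case monthly monitoring will continue". Extra levels may be drawn when there is a medical reason.
- **Section XIV, Determination of lithium levels.** Monthly for the first six months and quarterly after that. No drug class is excepted.
- **Table 6.** Section XIV makes this the visit schedule. After month 6 the lithium row is marked at month 9 only. Months 7-8 and 10-11 are blank, and no footnote mentions these drugs. The phone-visit footnote lets alternate visits in months 7-8 and 10-11 be done by telephone, and excepts only participants of childbearing potential.

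Table 5 lists diuretics, ACE inhibitors and angiotensin II receptor antagonists together as drugs that increase lithium levels.

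**The concern.** The stricter rule sits in a rationale paragraph of the eligibility section. The places a site coordinator would use to book blood draws (the dosing section, the follow-up section and the visit table) either leave out AR blockers or leave out the rule entirely. A site that follows those places exactly draws fewer levels than Section V requires, in a group singled out for closer monitoring.

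The omission does not look deliberate. Section V pairs ACE inhibitors with AR blockers both for admission and for mid-study starts, Table 5 puts them under the same heading, and no reason is given for a longer interval for AR blockers.

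The safety margin is narrow. The target is 0.6 to 0.8 mEq/L, Section XIII treats 1.2 as potentially dangerous, and Section XII gives 1.5 as the level from which lithium may be toxic. Table 6 also leaves creatinine blank in months 7-8 and 10-11, so no scheduled renal test fills the gap.

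**Working it through.** There is no plan figure to reproduce. The check is a count of scheduled lithium levels in months 7 to 11, after the monthly phase that applies to everyone and before the end-of-study visit.

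**Inputs**

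- Monthly rule: levels at months 7, 8, 9, 10 and 11, which is 5.
- Quarterly rule from month 6: the next levels fall at months 9 and 12, so 1 falls in months 7 to 11.
- Table 6 lithium row: months 7-8 blank, month 9 marked, months 10-11 blank, which is 1.
- Amiloride is a diuretic, so the Section XIII exception covers it. An AR blocker is neither an ACE inhibitor nor a diuretic, so it does not.

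**Levels scheduled in months 7 to 11**

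| Source | AR blocker | ACE inhibitor | Amiloride |
|---|---|---|---|
| Section V | 5 | 5 | 5 |
| Section XIII | 1 | 5 | 5 |
| Section XIV | 1 | 1 | 1 |
| Table 6 | 1 | 1 | 1 |

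**Shortfall against Section V**

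- AR blocker users: 5 − 1 = 4 levels (months 7, 8, 10 and 11) under each of Section XIII, Section XIV and Table 6.
- ACE inhibitor and amiloride users: 5 − 5 = 0 under Section XIII, and 5 − 1 = 4 under Section XIV and Table 6.
- Interval between scheduled levels after month 6: 1 month under Section V, and 9 − 6 = 3 months under the quarterly rule.

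So there are two separate faults. For AR blocker users, two operative rules (Sections V and XIII) disagree. For the other two classes those rules agree, and the fault is that Section XIV and the visit table do not repeat them.

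**The case against.** The best reply is that Section V is the specific rule for AR blocker users, while in Section XIII they fall only under the general quarterly default. On the usual principle the specific rule governs. Section XIII also sets no maximum, so a site that draws monthly complies with both sections. This stands as a way to read the protocol, and a careful site could reach it. It does not remove the contrary text: Section XIII names who stays on monthly levels, AR blockers are missing from it, and the visit table agrees with the omission.

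The second reply is that other safeguards exist, and they do reduce the risk:

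- Section XII expects regular levels when interacting drugs are taken.
- Section XIII allows extra levels for medical reasons.
- Providers are asked to report new drugs.
- Table 6 has a side-effect checklist and a medication review at every visit in this period.
- Section VIII tells sites to lower, hold or stop study drug when in doubt.
- The DMC reviews levels of 1.3 or more for a link with blood-pressure drugs.

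These are discretionary, triggered by an event, or without a stated interval. None sets the routine interval after month 6, and the DMC review depends on levels having been drawn.

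A reader might also infer that mid-study starters are left without a plan, or that Section V points to the wrong place for them. The documents do not support that. The section on ongoing dose adjustments covers changes in medication, has the Site Physician "obtain blood for lithium level and other determinations as needed", and continues monitoring until levels stabilise. The titration section also lists "new prescriptions of medications with potential drug-drug interactions" among reasons to lower the dose and, for a stable patient, says "the reduced dose will be maintained for approximately 5-7 days at which time another lithium level will be obtained". What remains for starters is the same AR blocker omission from the monthly rule.

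Last, Table 1 of the SAP still lists ACE inhibitors and angiotensin II receptor antagonists as exclusions. That is a separate inconsistency. This point rests on the protocol's eligibility text, and mid-study starters would be affected either way.

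**Conclusion.** The point holds as an internal conflict in a safety schedule. Under Sections XIII and XIV and Table 6 as written, an AR blocker user has 1 scheduled level in months 7 to 11 where Section V requires 5. ACE inhibitor and amiloride users are settled at monthly levels by Sections V and XIII, but Section XIV and Table 6 do not show it.

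A reader might extend the count to month 12 and report a shortfall of 5 of 6, because Table 6 has no end-of-study level (6 monthly levels against 1). That overstates it. The end-of-study blank applies to every participant, and at that visit the assignment is disclosed and care is handed over. The loss specific to this point is four levels.

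The conclusion assumes that the monthly rule in Section V applies at least to the three classes named just before it. The sentence immediately before the rule refers to antihypertensive users generally, so its reach may be wider; AR blocker users are included on either reading. The count also assumes steady state by month 6 and continued study medication. The number of participants affected cannot be worked out from the documents. The primary analysis, power and alpha are untouched. This should be corrected for safety and consistency, and it does not bear on the efficacy conclusion.

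**What to change.** 1. In Section XIII, Study medications, reword the exception to cover *an ACE inhibitor, an AR blocker or a diuretic (amiloride), whether taken at baseline or started during the study*.
2. Repeat the same exception where Section XIV states the lithium-level frequency.
3. Add a Table 6 footnote requiring a lithium level at months 7, 8, 10 and 11 for these participants while they are taking study medication. Month 9 is already marked.
4. Amend the Table 6 phone-visit footnote so that these participants still have blood drawn, at the site or at a community clinic (Section X allows this), in months when the visit is by phone. Without this, the new footnote would conflict with the existing one.

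If the Section V rule is meant to cover all antihypertensive users, the new wording should say so, so that the edit does not narrow it.

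The cost is mainly wording. Compared with Table 6 it means up to four more draws per affected participant and fewer visits done purely by phone, but Section V already requires those draws. No change to the SAP or the sample size follows from this point.
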